#### 4 STUDY DESIGN

#### 4.1 DESIGN

Randomized, double-blind, placebo-controlled clinical trial, parallel design

- Intervention Arm: Ciclesonide 600mcg BID inhaled with aero chamber *plus* intranasal ciclesonide 200 mcg DIE for 14 days. The aerochamber is Respichamber from the hospital which will be discarded after the 14 days. For information on how to use the aerochamber please refer to:
  - https://www.youtube.com/watch?time continue=1&v=O92 Ftf6Wnk&feature=emb title
- Control Arm: Placebo inhaled BID with respichamber (same as above) *plus* intranasal saline DIE for 14 days.

In Canada we will be using inhaled Ciclesonide (DIN 02285614 / Alvesco) and intranasal Ciclesonide (DIN 02303671 / Omnaris) as the active drug and a placebo inhaler (NDC 70515-710-01) as the placebo.

At present, all these products are sourced from Canadian wholesale distributors.

## 4.2 Study participant duration

- 14 days consisting of internet-based virtual visits
- Observational follow up at day 29 to assess final outcome status of hospitalization and SAE.

#### 4.3 Study procedures

- All procedures will consist of internet-based questionnaires completed by self-report.
- Informed consent is provided to access medical records to verify information, as necessary and in accordance with individual provincial laws.

#### 4.4 Individually identifiable health information:

Name, date of birth, phone number and address will be collected centrally at the RI-MUHC to prescribe study medication. These names and addresses will be communicated to approved study sites in other provinces to facilitate timely prescription and local shipping in each participating province. Email addresses will be collected for communication. If participants are hospitalized, the hospitalization date will be collected. **NO IDENTIFIABLE HEALTH INFORMATION WILL BE TRANSMITTED OUTSIDE OF CANADA.** 

# 4.5 Substudies (if applicable)

Additional sub-studies will undergo separate IRB approval, and these studies will involve separate informed consent. Consented participants will be queried as to if they wish to participate in future research.

# **4.6** Participation in concomitant clinical trials

Because of unknown potential drug-drug interactions between ciclesonide and other investigational products we will ask participants not to enroll in other clinical trials for the study duration.

# 5 STUDY ENROLLMENT AND WITHDRAWAL

Participants will undergo screening via REDCap.. The screening and inclusion criteria will be based on self-report.

# **5.1** Subject Inclusion Criteria

- Symptomatic COVID-19 disease (fever, cough OR shortness of breath) AND confirmed diagnosis with PCR+ SARS-CoV-2 within <= 6 days of enrolment (day 6 if same day shipping geographically permits)
- Shortness of breath is defined by self report as "shortness of breath", "chest tightness" or "chest congestion"
- Cough is defined as "dry cough" or "wet cough" by self report
- >= 18 years of age
- Provision of informed consent
- Mild symptomatic SARS-CoV-2 disease is defined as individuals who are SARS-CoV-2 PCR positive AND present with more than one symptom listed on the symptom checklist developed by the National Institute of Health MESA COVID-19 questionnaire (Version dated 04/10/2020; symptom checklist page 8) at study entry (see Appendix 2).

# **5.2** Subject Exclusion Criteria

- Already on inhaled corticosteroid medication
- Currently using systemic steroids (oral or intravenous or intramuscular such as Prednisone) or use of steroids 7 days prior to enrolment
- Severely ill patients at enrollment (i.e., admitted to ICU at admission)
- Unable to self-administer the inhaler
- Anticipated transfer to another hospital within 72 hours which is not a study site
- Known or suspected pregnancy and breastfeeding
- Known allergy to study medication or its components (non-medicinal ingredients; including lactose allergy (type I))
- Patients with untreated fungal, bacterial or tubercular infections of the respiratory tract
- Current hospitalization
- Current use of oxygen at home or in hospital
- Vaccinated for COVID-19

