#### 2.2 Rationale

Current standard of care is supportive care after the diagnosis of COVID-19.

Ciclesonide is a corticosteroid currently used for asthma (in its inhaled form) and nasal rhinitis (in its spray form). It has a very good safety profile. Much higher doses of ciclesonide (up to a single inhalation of 3200 mcg) have been administered to healthy volunteers and were well tolerated (9). As such, inhaled and nasal ciclesonide at the doses of 600mcg BID for 2 weeks will have few adverse events. The usual doses for ciclesonide are:

Standard asthma treatment (ciclesonide, *Alvesco*):

- The recommended dose range for ciclesonide in inhalation is 100 to 800 mcg daily (9).
- The recommended starting dose for most asthmatic patients is 200 mcg daily in Canada (10).
- The maximum dose of 800 mcg daily should be administered as 400 mcg twice daily (9).

Standard allergic rhinitis treatment (ciclesonide, *Omnaris*) (11):

- The recommended dose of OMNARIS is 200 mcg per day administered as 2 sprays (50 mcg/spray) in each nostril once daily.
- The maximum total daily dosage should not exceed 2 sprays in each nostril (200 mcg/day)

As the specific dose of ciclesonide to decrease SARS-CoV-2 is unknown, we planned to give a higher dose than the maximum approved dose for asthma of inhaled ciclesonide (1200 mcg daily administered as 600 mcg twice daily) plus the usual dose of intranasal ciclesonide (200 mcg/day) for 14 days. Given viral replication begins in the nasal cavity and then progress to the lungs, we have chosen to administer ciclesonide both intranasally and inhaled. This dose has been chosen in order to maximize deposition of the study drug in the lower airways. Although the usual dose of ciclesonide for asthma is 400 mcg twice daily (for a total of 800 mcg/day), single doses (up to 3200 mcg) have been administered to healthy subjects without significant side effects (9).

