#### **Uncommon Clinical Trial Adverse Drug Reactions (≥0.1% to <1%)**

Cardiovascular: Palpitations (0.1%).

Eye: Cataract subcapsular (0.1%).

Gastrointestinal: Nausea (0.2%), Dry mouth (0.1%), Dyspepsia (0.1%)

Infections: Oral candidiasis (0.6%), Candidiasis (0.1%), Oral fungal infection (0.1%),

Pharyngitis (0.1%).

Injury: Contusion (0.1%).

Investigations: ALT increased (0.1%), Gamma-glutamyltransferase increased (0.1%)

Weight increased (0.1%)

Nervous System: Headache (0.4%), Dysgeusia (0.3%), Dizziness (0.1%).

Respiratory, thoracic and mediastinal disorders: Pharyngolaryngeal pain (0.4 %), Throat irritation (0.3%), Dry throat (0.1%).

Skin: Rash (0.1%).

The incidence of local oropharyngeal adverse reactions in ALVESCO-treated patients was low and comparable to placebo.

The risk of thrush (appearance of Candida albicans in the mouth and throat) is rare but can be further reduced by the use of an aerochamber and a proper mouth rinsing after using Ciclesonide.

The contraindications to Ciclesonide, as listed on the monograph:

CONTRAINDICATIONS ALVESCO (ciclesonide) is contraindicated in patients with known hypersensitivity to any of the ingredients.

ALVESCO is not to be used in the primary treatment of status asthmaticus or other acute episodes of asthma, or in patients with moderate to severe bronchiectasis.

OMNARIS (ciclesonide) is contraindicated in patients with hypersensitivity to any of the ingredients.

OMNARIS should be used with caution, if at all, in patients with active or quiescent tuberculosis infections of the respiratory tract.

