# 6.2 Dosage, Preparation, and Administration of Investigational Product

6.2.1 Drug/Device Handling: Omnaris (aqueous nasal ciclesonide) and Alvesco (aerosol oral ciclesonide) or placebo will be dispensed by the Research Pharmacy in each approved center. The RI-MUHC will do this for the province of Quebec. To do so, the study investigators will send a prescription to the Pharmacy, the pharmacy will dispense the appropriate study medicine. The medicine will then be provided to research volunteers via FedEx / courier delivery in the province of approval (e.g. within Quebec for RI-MUHC).

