# 7 STUDY SCHEDULE

- Information includes consent document. The patient signs electronically in the application after answering questions which confirm comprehension.
- If eligible, drug is prescribed, they are randomized, and shipping is arranged for study drug or placebo

Questionnaire	Day 0	Day1	Day 3	Day 5	Day 7	Day 10	Day 14	Day 29
Eligibility (screening form)	X							
Enrolment form (for eligible patients)	X							
Follow up questionnaire (MESA COVID 19)	X	X	X	X	X	X	X	X
Severity of overall symptoms	X	X	X	X	X	X	X	X
Dyspnea characteristics	X	X	X	X	X	X	X	X
Dyspnea severity	X	X	X	X	X	X	X	X
Visual analog scale for individual symptoms	X	X	Х	X	X	X	Х	X
Sleep PROMIS scale	X	X	X	X	X	X	X	X
Anxiety PROMIS scale	X	X	X	X	X	X	X	X

WHO ordinal scale	X	X	X	X	X	X	X	X
Hospitalization/Oxygen		X	X	X	X	X	X	X
use query								
Side effects query		X	X	X	X	X	X	X
Mortality							X	X
Subject orientation of							X	
the type of the study								
drug (placebo or active								
drug)								

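### Moderate to severe bronchiectasis is listed as a contraindication to inhaled ciclesonide in section 2.3.1 but is missing from both exclusion lists

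*Combined protocol and SAP*

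**What the plan says.** Section 2.3.1 closes with contraindications taken from the product monograph. For the inhaled product it states that "ALVESCO (ciclesonide) is contraindicated in patients with known hypersensitivity to any of the ingredients". The next sentence says that the product is not for primary treatment of acute asthma "or in patients with moderate to severe bronchiectasis".

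The exclusion criteria appear in the Summary and again in section 5.2. Both lists contain "Known allergy to study medication or its components", and both contain "Patients with untreated fungal, bacterial or tubercular infections of the respiratory tract". Neither mentions bronchiectasis.

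Screening is an online self-report questionnaire (sections 5 and 7.1). Under section 7.2.1 a central physician reviews the screening form and medication list. The patient is telephoned if there is any doubt about suitability, and an unacceptable review leads to exclusion before randomisation. An investigator prescribes: section 6.2 says that "the study investigators will send a prescription to the Pharmacy, the pharmacy will dispense the appropriate study medicine", and section 7 gives the sequence as "If eligible, drug is prescribed, they are randomized, and shipping is arranged for study drug or placebo".

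**The concern.** A condition that the protocol's own risk section gives as a reason not to use the inhaled product should normally be an explicit exclusion. Here one contraindication from that text reached the eligibility criteria and another did not. The section on the rationale for the criteria discusses timing of treatment and baseline laboratory testing, and gives no reason for the difference.

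What is at stake is the safety of individual participants. The trial runs without in-person visits: drug is couriered and follow-up is by questionnaire. The written criteria and the screening form therefore carry more of the protective load than they would in a clinic-based trial. A patient with stable bronchiectasis could meet every written rule and be sent active drug.

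**Working it through.** No arithmetic applies. The check sets the contraindication text against the eligibility text and then follows one patient through the process.

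**Step 1. Contraindication statements in section 2.3.1 against the two exclusion lists**

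| Statement in 2.3.1 | Summary list (10 items) | Section 5.2 list (11 items) |
|---|---|---|
| Inhaled product: hypersensitivity | Covered by the allergy item | Covered by the allergy item |
| Inhaled product: acute asthma | Limits the indication; not relevant to treating COVID-19 | Same |
| Inhaled product: moderate to severe bronchiectasis | Not named | Not named |
| Nasal product: hypersensitivity | Covered by the allergy item | Covered by the allergy item |
| Nasal product: caution in tuberculosis of the respiratory tract | Partly covered (untreated infection) | Partly covered (untreated infection) |

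The two lists differ by one item, anticipated transfer to a hospital that is not a study site, which has no bearing here. Bronchiectasis is named in 0 of 10 and 0 of 11 items. Section 2.3.1 is the only place in the document where the word occurs. The tuberculosis wording is only a caution, yet part of it was carried over. That makes the bronchiectasis omission look like an oversight, although the documents do not say so.

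**Step 2. Do other exclusions cover it indirectly?** Current inhaled corticosteroids, current or recent systemic steroids, oxygen use and untreated respiratory infection would each remove some patients with bronchiectasis. None is equivalent to the condition.

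**Step 3. Follow one patient.** Take a symptomatic, PCR-positive, unvaccinated adult at home, within the enrolment window, with stable moderate bronchiectasis. The patient takes no steroids, uses no oxygen, has no untreated infection and meets no other exclusion.
- Inclusion criteria (section 5.1): met.
- Exclusion criteria (Summary and section 5.2): none applies.
- Appendix B: all inclusion and no exclusion criteria, so satisfied. These are necessary conditions only; passing them does not guarantee admission.
- Physician review (section 7.2.1): would stop the patient if the form asks about the condition, if a medicine suggests it, or if something else prompts a call that brings it out.
- Prescription (sections 6.2 and 7): a further clinical step, with no mention of the condition.

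The outcome therefore turns on the content of the screening form, which is not reproduced, and on clinical judgement.

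**The case against.** The strongest reply is that medical review already handles this. Every participant's form and medication list is read by a physician, and an expert in internal medicine checks the medication list. Doubts lead to a telephone call, unsuitable patients are excluded with the reason recorded, and a study investigator prescribes. Those clinicians have the contraindication in their own protocol. Consent also allows access to medical records to verify information where necessary. This is a real safeguard and it stands as mitigation. It does not fully close the gap, because the call needs a doubt to trigger it and no step names the condition.

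Three stronger readings are tempting, and the documents support none of them.

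- A reader might infer that screening does not ask about bronchiectasis. The form is not reproduced, so this cannot be concluded. The text establishes only the absence from the two lists.
- A reader might infer that the physician and prescriber are confined to what the form shows them. The telephone call in section 7.2.1 is a route to more information.
- A reader might infer that the dose enlarges this particular risk, since section 2.2 says "we planned to give a higher dose than the maximum approved dose for asthma of inhaled ciclesonide". That dose applies to every participant on active drug, and nothing in the documents links dose to harm in bronchiectasis. The same section also reports that much higher single doses were tolerated by healthy subjects, which is limited reassurance. The dose does not measure the size of this problem in either direction.

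It can also be said that enrolment may be over. Section 9.5 describes the DSMB meetings in the past tense and says that enrolment dropped off. If so, amending the lists protects nobody, and only the records check remains useful.

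**Conclusion.** The omission is certain from the text: the contraindication is stated, and neither exclusion list contains it. Whether anyone with the condition was or would be randomised is unknown. The documents give no prevalence and no rate of harm, so no number is estimated. Given the partial exclusions and the physician review, the number is probably small and may be zero. With equal arms (159 of 318), about half of any such participants would be expected to receive active drug.

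This is a low-severity inconsistency between the risk section and the eligibility criteria. It has no bearing on the primary analysis, the sample size or the error rates. The conclusion rests on reading the bronchiectasis wording as a patient-level contraindication, which follows from its place under that heading, and it makes no assumption about what the screening form contains.

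**What to change.** If recruitment is open, add moderate to severe bronchiectasis to the exclusion criteria in both the Summary and section 5.2. Put a direct question about it on the REDCap screening form, so that the reviewing physician sees the answer before randomisation. If the form already asks, only the two list entries are needed. The cost is a short amendment, one question and a few extra screen failures.

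If recruitment has ended, check the screening forms and medication lists already held, report any participant with the condition, and state whether the question was asked. Without that last statement a count of zero cannot be interpreted. The cost is a limited records check and a sentence in the report.

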#### Rationale for inclusion / exclusion criteria:

Mean Incubation period is  $\sim$ 5.2 days, thus we wish to limit enrollment such that delivery of the study medicine occurs in the time period in which it can ameliorate disease (i.e. start

of study medicine by <=6 days after positive PCR). Day 6 only if able to ship the drug and commence it the same day as receiving it.

In clinical practice, oral and nasal ciclesonide is prescribed without any baseline laboratory testing or monitoring.

#### **5.3** Treatment Assignment Procedures

#### **5.3.1** Randomization Procedures

Participants will be randomized via permuted block randomization. Randomization will be created and recorded on an electronic log. Study investigators and subjects will be blinded.

## **5.3.2** Masking Procedures

Participants will be provided masked study medicine, shipped by courier (e.g. FedEx). The intervention vs. placebo will not be identical; however, participants and outcome assessors will be masked to their assignment.

#### **5.3.3** Subject withdrawal criteria

Participants may withdraw at any time point at their discretion. Subject withdrawal is defined as decision to terminate trial treatment. Subject will be replaced until the targeted 318 patients required for our power calculation. Study recruitment will be on a rolling basis. Our accrual ceiling is 2 times the required number of participants for the study. Based an alpha of 0.05 and a 15% subject dropout rate, we require 159 participants per arm. Our current power calculations account for a 25% subject dropout rate. As such, should individuals drop out (ie. be lost to follow up), it is unlikely to affect the study error.

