#### **5.3.4** Handling of Withdrawals

Patients who discontinue the study drug will be encouraged to stay on study and will continue to be followed for safety and efficacy endpoints, unless they have withdrawn consent.

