## **11.2** Sample Size Considerations

Our primary outcome is the proportion of patients with resolved respiratory symptoms (fever, cough, shortness of breath, chest congestion or chest tightness) at day 7.

This study is powered based on determining if there is a 15% increase in our primary outcome, the proportion of participants with no symptoms of shortness of breath (including chest congestion and chest tightness), cough or fever at Day 7. Based on the assumption that, by Day 7, 65% of untreated subjects, and 80% of treated subjects, will have resolved their symptoms, we will need 159 subjects per group to detect this difference with 80% power (5% alpha). This analysis has been adjusted to include a 15% dropout rate. The total number of study participants required is 318. These assumptions were made based on another outpatient RCT evaluating symptoms in COVID-19(15).

% Resolved by Day 7- Placebo arm	% Resolved by Day 7- Treatment arm	Proportion difference	Nominal Power, p=0.05	Total participants	Total participants including 15% drop out
75%	85%	10%	0.8	250	
75%	90%	15%	0.8	200	
75%	95%	20%	0.8	98	
70%	80%	10%	0.8	586	
70%	85%	15%	0.8	240	
70%	90%	20%	0.8	124	
70%	95%	25%	0.8	70	
65%	75%	10%	0.8	656	
65%	80%	15%	0.8	276	318 (159 per arm)
65%	80%	15%	0.9	368	
65%	85%	20%	0.8	144	
65%	90%	25%	0.8	86	
60%	70%	10%	0.8	712	
60%	75%	15%	0.8	304	
60%	75%	15%	0.9	406	
60%	80%	20%	0.8	162	
60%	85%	25%	0.8	98	
60%	90%	30%	0.8	62	

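### Section 5.3.3 claims the power calculations cover 25% dropout, but 318 allows only for 15%; with 318 randomised and not replaced, 25% loss leaves about 74–75% power

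*Combined protocol and SAP*

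**What the plan says.** Section 5.3.3 (Subject withdrawal criteria) makes these statements in sequence:

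- on replacement: "Subject will be replaced until the targeted 318 patients required for our power calculation";
- on the ceiling: "Our accrual ceiling is 2 times the required number of participants for the study";
- on the basis of the sample size: "Based an alpha of 0.05 and a 15% subject dropout rate, we require 159 participants per arm";
- in the next sentence: "Our current power calculations account for a 25% subject dropout rate";
- and, as the consequence: "should individuals drop out (ie. be lost to follow up), it is unlikely to affect the study error".

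Section 11.2 (Sample Size Considerations) assumes that symptoms resolve by day 7 in 65% of untreated and 80% of treated participants, with 80% power and 5% alpha. It says "This analysis has been adjusted to include a 15% dropout rate". Its table gives 276 in total before dropout and 318 (159 per arm) after. No calculation in the document uses 25%.

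Section 5.3.3 defines withdrawal as stopping trial treatment. Section 5.3.4 says people who stop the drug "will continue to be followed for safety and efficacy endpoints" unless they withdraw consent. Section 11.4 analyses them as intent-to-treat, and limits the primary analysis set to participants who were shipped drug, took a dose and completed at least one follow-up assessment.

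**The concern.** Two dropout rates are given, one sentence apart, for the same sample size, and only one can be the rate behind 318. The second is more than a stray figure, because the protocol draws a conclusion from it: readers are told that losses on that scale should not matter. Random loss leaves the type I error alone but raises the type II error. If the 25% allowance is not in the number, an ethics board or monitoring committee could watch attrition climb towards a quarter in the belief that power was protected. Follow-up here is remote and self-reported, so attrition is a practical matter for this trial.

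**Working it through.** **Inputs.** From section 11.2: p₁ = 0.65, p₂ = 0.80, difference 0.15, power 80%, alpha 5%, 15% dropout, 276 before and 318 after inflation. From section 5.3.3: 15%, 25% and 159 per arm. Sidedness is not stated. I take two-sided, because it reproduces the table; one-sided 5% would give 109 per arm, 218 in total.

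**Step 1: reproduce the plan's figure.** With pooled variance (mean proportion 0.725) and no continuity correction:

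n = [1.960 × √(2 × 0.725 × 0.275) + 0.8416 × √(0.65 × 0.35 + 0.80 × 0.20)]² / 0.15²
= (1.2377 + 0.5239)² / 0.0225 = 137.9, so 138 per arm, **276** in total. This matches the table exactly.

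**Step 2: which dropout rate gives 318?**

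| Rate | N × (1 + rate), the plan's method | N / (1 − rate) |
|---|---|---|
| 15% | 276 × 1.15 = 317.4 → **318** | 138/0.85 → 163 per arm, 326 |
| 25% | 276 × 1.25 = 345 → 346 | 276/0.75 = 368 |

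Only 15% gives 318. Neither method gives 318 at 25%.

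**Step 3: power with 318 randomised, none replaced, lost participants excluded.** For m evaluable per arm:

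- pooled: Φ[(0.15√m − 1.2377) / 0.6225]
- unpooled: Φ[0.15√m / 0.6225 − 1.960]

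| Situation | m per arm | Pooled | Unpooled | Exact enumeration (m rounded down) |
|---|---|---|---|---|
| 15% lost | 159 × 0.85 = 135.15 | 79.2% | 80.0% | 79.6–79.7% |
| 25% lost | 159 × 0.75 = 119.25 | 74.0% | 74.9% | 74.4–75.0% |
| 318 evaluable | 159 | 85.3% | 86.0% | 85.7–85.8% |

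Worked pooled case at 25%: 0.15 × √119.25 = 1.6380; (1.6380 − 1.2377)/0.6225 = 0.643; Φ = 0.740.

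**Step 4: the loss that 318 can absorb at 80% power.** Pooled: 1 − 137.91/159 = 13.3%. Unpooled, where 135.18 per arm are needed: 1 − 135.18/159 = 15.0%.

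**Step 5: the rest of the table.** For 75% vs 85% the pooled formula gives 249.98, so 250 per arm and 500 in total. The table row reads "75% 85% 10% 0.8 250", with 250 in the column for total participants. A total of 250 (125 per arm) has 50.7% power. All other rows reproduce to within 2 participants. This row does not feed 318.

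**The case against.** The strongest reply is that the 74–75% figure needs a condition the text seems to point away from. Section 5.3.3 provides for replacement up to 318, with a ceiling of twice the required number (2 × 318 = 636). If everyone lost were replaced until 318 were evaluable, power would be about 85%. This is why the power loss is stated only conditionally. It does not rescue the sentence. Replacement is tied to withdrawal, and withdrawal is defined as stopping treatment, while people who stop treatment remain in follow-up and analysis. Whether those lost to follow-up are replaced is not said. An inflation for dropout suggests that 318 counts randomised participants; replacement up to 318 suggests the opposite. On either reading, no calculation contains a 25% allowance.

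A second reply is that lost participants may not all leave the denominator. Someone who answers on day 3 but misses day 7 stays in the modified intention-to-treat set, and section 11.4 does not say how a missing day 7 outcome is scored. This stands as a limit on the power figures. Scoring such participants as unresolved would lower power further. At 25% missing in each arm the rates become 0.65 × 0.75 = 48.75% and 0.80 × 0.75 = 60%, and the pooled formula with 159 per arm gives about 52%.

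It is also fair to say that the text claims dropout is unlikely to matter rather than that it cannot, and that neither 318 nor the analysis method changes.

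**Conclusion.** The concern holds. Section 5.3.3 attributes to the design a 25% dropout allowance that it does not have, and rests a reassurance on it. With 318 randomised, not replaced, and lost participants excluded and missing at random, power at 25% loss is 74–75%, so type II error is 25–26% against the planned 20%. Two-sided 5% is an assumption, supported by the exact match to 276.

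At 15% loss the shortfall (79.2% to 80.0%) is negligible and is not counted as an error. The withdrawal, follow-up and analysis rules can coexist, but what 318 counts is left open, and the answer moves power at 25% loss between about 74% and about 85%. The 75% vs 85% table entry is a separate, minor error. This should be fixed, and wording is enough.

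**What to change.** 1. State in sections 5.3.3 and 11.2 whether 318 counts randomised or evaluable participants. Settle this first, because the next items depend on it.
2. In section 5.3.3, delete the 25% sentence and the conclusion drawn from it. Use 15% in both sections.
3. If 318 means randomised, add a sentence such as: With 318 participants randomised and not replaced, and those lost excluded from the analysis, power is about 79% at 15% loss and about 74% at 25% loss (65% vs 80%, two-sided 5%). If 318 means evaluable, state instead that power is about 85%.
4. Reword the replacement sentence to match item 1, saying whether it applies to participants lost to follow-up and noting that those who stop treatment stay in follow-up and analysis, as sections 5.3.4 and 11.4 provide.
5. In the section 11.2 table, change the 75% vs 85% total from 250 to 500.

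If 318 means randomised, the cost is wording only, and the protocol gives up its claim of protection at 25%. The alternative is to cover 25% in fact, which raises the total by 28 to 50 participants (346 − 318 = 28; 368 − 318 = 50). That is within the ceiling of 636, but section 9.5 records that enrolment dropped off, so it may not be practical. The correction does not depend on it.

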#### **9.2.3** Serious Adverse Events (SAEs)

SAEs (e.g. hospitalization) will be followed for up to 29 days to assess final outcome.

A patient who reports hospitalization and/or an adverse effect of the study drug on a CRF who has not reached out to the team by phone or email will be contacted in a timely fashion and the site doctor made aware. We will review the "positive" CRFs to detect these. We also collect details about the hospitalization.

Patients who do not complete their day 14 CRF will receive reminder emails and, if they do not respond to that, they will be telephoned. Patients must provide an alternate contact at enrollment. If they do not respond to the above means, we will call that contact to find out what has happened. If that person does not know or is not available, we will send registered mail to the address of the patient before concluding loss to follow-up. A sensitivity analysis of the mortality outcome will be performed assuming patients lost to follow-up despite these means have died.

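### Section 5.3.3 says the power calculations cover 25% dropout, but 159 per arm carries only the 15% allowance of section 11.2; at 25% unreplaced loss power is about 74%, not 80%

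*Combined protocol and SAP*

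**What the plan says.** Section 5.3.3 gives two dropout allowances for one sample size, in consecutive sentences. The first reads "Based an alpha of 0.05 and a 15% subject dropout rate, we require 159 participants per arm". The second reads "Our current power calculations account for a 25% subject dropout rate". From the second the section concludes that, "should individuals drop out (ie. be lost to follow up), it is unlikely to affect the study error".

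Section 11.2 gives only one allowance: "This analysis has been adjusted to include a 15% dropout rate. The total number of study participants required is 318". Its table shows 276 participants before dropout for 65% versus 80% at 80% power, and 318 (159 per arm) in a column headed with 15%.

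Section 5.3.3 also provides for replacement: "Subject withdrawal is defined as decision to terminate trial treatment. Subject will be replaced until the targeted 318 patients required for our power calculation". The limit is generous: "Our accrual ceiling is 2 times the required number of participants for the study". Under section 5.3.4, patients who discontinue the drug "will continue to be followed for safety and efficacy endpoints, unless they have withdrawn consent".

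**The concern.** The 25% sentence is more than a stray figure, because the plan draws a conclusion from it. A reader is told that up to a quarter of participants could be lost with little effect on the error rates. If the sample size was built for 15%, that assurance is false as written, and someone weighing a null result could wrongly set attrition aside as an explanation.

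The design makes this worth getting right. Follow-up is by internet questionnaire and self-report, so silent non-response is a plausible way to lose the Day 7 outcome. Section 5.3.3 mentions people lost to follow-up only in the sentence that says they are unlikely to matter.

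**Working it through.** **Inputs.** From section 11.2: 65% resolved on placebo, 80% on treatment, 80% power, 5% alpha, 276 before dropout, 318 after. Allocation is equal (159 per arm). The sample-size text does not say whether the test is one- or two-sided. Two-sided is assumed here because it agrees with the 95% CI in section 11.4 and reproduces the table (a one-sided test would need only 109 per arm). Loss is assumed equal in the two arms.

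**Reproducing the plan's figure.** With p̄ = (0.65 + 0.80)/2 = 0.725, let

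- A = √(2 × 0.725 × 0.275) = 0.6315
- B = √(0.65 × 0.35 + 0.80 × 0.20) = 0.6225

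Then n per arm = [(1.960 × A + 0.842 × B)/0.15]² = 137.9, so 138 per arm and 276 in total, which matches the table. Multiplying by 1.15 gives 276 × 1.15 = 317.4, taken to 318, or 159 per arm, which also matches. The stated target is therefore a 15% calculation.

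**Could 318 also be a 25% calculation?** No. By the plan's own multiplication, 25% would give 276 × 1.25 = 345 (346 with equal arms). By division it would give 138/0.75 = 184 per arm, or 368.

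**Power after loss.** Take 318 randomised, no Day 7 outcome from those lost and no replacement. Power = Φ[(0.15 × √n − 1.960 × A)/B], with n the number per arm who have an outcome:

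| Loss | n per arm | Power |
|---|---|---|
| 0% | 159 | 85.3% |
| 13.2% | 138 | 80.0% |
| 15% | 159 × 0.85 = 135 | 79.1% |
| 20% | 159 × 0.80 = 127 | 76.6% |
| 25% | 159 × 0.75 = 119 | 73.9% |

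At 25% loss the type II error is 26.1% instead of 20%, and the difference detectable with 80% power is 16.0 points instead of 15.0. The 13.2% row is 1 − 138/159. It falls short of 15% because the plan multiplied by 1.15 instead of dividing by 0.85 (138/0.85 gives 163 per arm). That costs less than one point of power.

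**Sensitivity to the formula.** At 119 per arm, the unpooled version gives 74.8%, the arcsine version 74.3% and the continuity-corrected version 68.9%. None reaches 80%.

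**How much replacement could offset.** Suppose a share s of participants stop treatment, stay in follow-up and are replaced, so that 318/(1 − s) are randomised, and 25% are then lost without an outcome. The documents give no value for s, so these are assumptions:

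- s = 5%: about 335 randomised, 125.5 per arm with an outcome, power about 76%
- s = 10%: about 353 randomised, 132 per arm, power about 78%
- s = 13.6%: about 368 randomised, 138 per arm, power about 80%

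**The case against.** The strongest reply is that the figure of 74% switches off part of the plan. Section 5.3.3 provides for replacement, recruitment is rolling, and the ceiling is 2 × 318 = 636. The same paragraph equates dropping out with being lost to follow-up, so it may be meant to replace those people too. This stands to a point: 74% is a no-replacement figure, and the 15% allowance plus replacement gives the reassurance some support. It does not rescue the 25% sentence. Replacement is not an allowance inside a power calculation, and its trigger is a decision to terminate treatment. That trigger takes in people who stay in follow-up and are still analysed, and it does not clearly take in people who go silent.

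A second reply is that the effect is modest. No document predicts 25% loss, and at the planned 15% power is 79%. The placebo rate matters about as much: at 119 per arm, power is 79.5% for 70% versus 85% and 69.7% for 60% versus 75%. All of that stands and bears on the size of the point. The sentence is still wrong.

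Third, the plan does anticipate heavy loss. Section 11.4, under the handling of withdrawn subjects, adds a secondary analysis with an unknown category if loss or discontinuation is large, and section 8.2 seeks consent to contact a provider or public health after loss to follow-up. These help with description and tracing, but they do not restore power for the primary comparison. The chase sequence in section 9.2.3 is tied to a later form: "Patients who do not complete their day 14 CRF will receive reminder emails". A reader might infer that Day 7 forms were never chased. Silence in a safety section does not show that.

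**Conclusion.** The 25% statement is wrong as written, and the reassurance drawn from it should not stand. The sample size of 159 per arm carries 15%, as the preceding sentence and section 11.2 both say. Under the stated conditions (318 randomised, equal loss, no Day 7 outcome from those lost, no replacement, two-sided 5%), power is about 79% at 15% loss, 77% at 20% and 74% at 25%. Replacement could recover some of this, by an amount the documents do not allow anyone to fix.

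Stronger readings are tempting but unsupported. A reader might infer that the target is too small or that the trial's power is 74%. The target agrees with the plan's own 15% assumption to within one point of power, and 74% applies only at a loss rate that the plan does not forecast. A reader might also infer that replacing people who stop treatment biases the comparison. It does not, since those who stay in follow-up are still analysed as randomised.

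**What to change.** In section 5.3.3, delete the 25% sentence and the conclusion that follows it, and use 15% throughout. In section 11.2, add one line giving power at 15%, 20% and 25% loss (about 79%, 77% and 74%), with its conditions: 318 randomised, none replaced, and no Day 7 outcome from those lost.

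The cost is wording only. The target stays at 318, and no new recruitment rule is asked for. In particular, extending replacement to Day 7 non-responders is not part of this fix: it would be a new rule, and adding participants cannot remove bias if non-response is related to outcome. Section 9.5 reports that enrolment dropped off. If fewer than 318 were randomised, the same formula should be applied to the number actually reached, because the three figures above would not then describe the trial.
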